Statistical Analysis Plan: Title Page

**Blood Loss and Visibility with Esmolol vs. Labetalol in Endoscopic Sinus Surgery: A
Randomized Trial**

Date: 09/04/2018

Study Summary and Aims

The purpose of this study is to compare esmolol and labetalol bleeding and visibility outcomes in FESS surgery. It is a double-blinded two-armed trial with no placebo control, conducted at a tertiary center. Participants include adults with history of CRS with or without nasal polyps, undergoing FESS for CRS. 38 patients were enrolled, with 32 receiving study drug (17 esmolol, 15 labetalol). Total study duration, including recruitment and analysis, was 1 year with no follow-up. Treatments involve giving intraoperative 20mg of Labetol (max dose = 300 mg for total operation) or infusing 0.1mg/kg/min esmolol (max dose after 30 minutes = 0.3mg/kg/min) when MAP rises above 80 mmHg. The primary aim is to evaluate the relative efficacy of these drugs in FESS surgery, specifically controlling bleeding and improving visibility.

Study Endpoints

March 2017 – March 2018 enrollment, drug administration only during surgery.

Sample Size Considerations

Futility analysis based on estimated blood loss data to see how many patients would be required to show significant differences in blood loss, and therefore mucosal visibility, between drug groups. Given the small differences in blood loss per minute during surgery between treatment groups (0.63 compared to 0.67), and given the relatively large standard deviations obtained (0.33 and 0.37), 1,245 patients would be required in each drug group (total N = 2,490), using a non-paired (two-sided) *t-test* for the comparison, to show a statistically significant difference between the 2 treatments with a power of 0.8 and type I error of 0.05.

These sample size calculations are based on the primary aims of determining a significant difference in FESS visibility between the two drugs.

The null hypothesis is that there will be no statistical difference between esmolol and labetalol in FESS visibility and bleeding parameters. The alternative hypothesis is that there will be a significant difference, in either drug, for improved FESS visibility and bleeding parameters.

The minimum difference that we judge to be statistically significant is a 1-point change on the visibility scores (Boezaart 5-point, Wormald 10-point).

Analysis Sets

N/A

Statistical Analysis and Description of Main Tables

All data for the study outcomes was analyzed with the Wilcoxon rank sum test, used to compare the confidence interval location shift differences between groups. P-value was based on asymptotic Wilcoxon two-sample test with continuity correction of 0.5. The 95% confidence interval for the location shift was based on Hodges-Lehmann estimation. Categorical data

(gender) analyzed with chi-square test. Results were analyzed using the statistical program IBM[®] SPSS[®] Statistics (Version 24). P-value < 0.05 was considered significant.

Table 1. Demographic Information and Baseline Characteristics of Study Patients

Characteristics	Group A (n=13)	Group B (n=15)	P-value
Age, years			
Mean (SD)			
Median (Q1, Q3)			
Male, No. (%)			
BMI, kg/m ²			
Mean (SD)			
Median (Q1, Q3)			
Lund-Mackay score [†]			
Mean (SD)			
Median (Q1, Q3)			
Septoplasty, No. (%)			

Figure 1. Trial profile

[figure not shown]

Table 2. Comparing Anesthesia and Surgical Parameters

Characteristics	Group A (n=13)	Group B (n=15)	P-value Location shift [†] (95%CI)
Duration, min			
Surgery			
Mean (SD)			
Median (Q1, Q3)			
Anesthesia			
Mean (SD)			
Median (Q1, Q3)			
PACU			
Mean (SD)			
Median (Q1, Q3)			
EBL, mL			
Mean (SD)			
Median (Q1, Q3)			
Rate of blood loss, mL/min			
Mean (SD)			
Median (Q1, Q3)			
Heart rate (bpm)			
Mean (SD)			
Median (Q1, Q3)			
Mean MAP			
Mean (SD)			
Median (Q1, Q3)			
Mean Boezaart score			
Mean (SD)			
Median (Q1, Q3)			
Mean Wormald score			
Mean (SD)			
Median (Q1, Q3)			

[†]Location shift = Group B – Group A

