Subjects who are scheduled for routine endoscopic sinus surgery will be recruited (n=40). The subjects in this prospective study will be randomized to either receive labetalol or esmolol. Current standard of care in preventing hypertension during sinus surgery due to stimulation and injection and application of sympathetic agents includes, narcotic administration, increasing volatile agent (Sevoflurane), esmolol, labetalol and other agents (hydralazine, nicardipine and nitroprusside). It is not known the impact these anti-hypertensive agents have on blood loss or blood in surgical field.

Intraoperatively, topical epinephrine pledgets will be used for decongestion similar to what is done routinely in endoscopic sinus surgery.

Intraoperative visibility will be scored utilizing two validated endoscopic visibility scores. In addition, at the end of surgery the estimated blood loss will be calculated by subtracting the amount of irrigation used during surgery from the amount of blood in the suction canisters.

In addition, the surgical video will be recorded and the intraoperative visibility will also be recorded by an independent observer.

In addition to the demographics and our primary outcome, secondary outcomes will be collected including duration of anesthesia, duration of surgery, final CO₂, postoperative bleeding, visit to the ED following discharge, need for medical attention following discharge, surgeon satisfaction on a likert scale (1-10), need for surgical re-intervention, and pain score after surgery, as well as time spent in recovery, use of anti-emetics postop, and nurses notes on as regards to pain and recovery.

Subjects may be excluded from the study if the anesthesiologist deemed it necessary that the protocol drug can not be used on the patient for any reason. Otherwise, it is expected that the surgeries will be routinely performed and the study outcome

variables do not interfere with the routine.

4. Study Procedures:

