This will be a prospective randomized study comprising subjects (n=40) over 18 years of age scheduled for ESS. The inclusion criteria will be male or female patients with ASA physical status 1 (normal otherwise healthy patient) or 2 (patient with mild systemic disease) and patients who have chronic sinusitis with or without nasal polyps. Exclusion criteria include: pregnancy, asthma, obstructive pulmonary diseases, sinus bradycardia and severe bradycardia, sick sinus syndrome, heart failure, end-stage renal disease, stroke, diabetes mellitus, preoperative use of nonsteroidal anti-inflammatory medications (NSAIDS) or aspirin (ASA) within the last week, and a body mass index (BMI) greater than 40. Additionally, any patient that the anesthesiologist deems unfit for randomization will also be excluded.

We will randomize the patients in blocks of 4 to determine the impact of a specific study drug (either esmolol (n=20) or labetalol (n=20) along with sevoflurane to control blood pressure on bleeding. The patients will be classified according to their Lund Mackay scores, which will be obtained from their routine CT scan performed prior to their surgery.

Written informed consent will be obtained. On arrival to the operating room, all the patients will be monitored as per usual anesthesia routine. Patients in both groups will be induced using 1-2 mg midazolam PRN anxiety, 1-3 mcg/kg fentanyl, 20-40 mg lidocaine, 1-2 mg/kg propofol, and 0.05-0.1 mg/kg vecuronium. Thereafter, maintenance with general anesthesia will receive 1-2% of sevoflurane (end expired). Both groups may receive fentanyl throughout the case at the discretion of the anesthesiologist. The dose of fentanyl is not to exceed 5 mcg/kg. The patient's mean arterial blood pressure (MAP) will be maintained at 70-80 mm Hg (80 for hypertensive patients) by first adjusting the sevoflurane concentration within their range (between 1-2 percent for the sevoflurane. If sevoflurane is maximized (Fe sevo >2%) and the target MAP is not achieved, then the patients will receive either esmolol or labetalol (study drug will be blinded for surgeon).

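### The SAP counts 32 treated patients (17 and 15) but heads its tables 13 and 15 and defines no analysis set: either a header is wrong or at least 4 treated patients are left out without a stated rule

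*SAP*

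**What the plan says.** The SAP, Study Summary and Aims, gives the flow as "38 patients were enrolled, with 32 receiving study drug (17 esmolol, 15 labetalol". The Analysis Sets section contains only N/A. The statistical analysis section says that all outcome data were analysed by the Wilcoxon rank sum test and names no population. The shells of Tables 1 and 2 both carry the column heads Group A (n=13) and Group B (n=15). The Table 2 footnote sets "Location shift = Group B – Group A", and no key links A or B to a drug. Figure 1 is titled as the trial profile, but its content is not shown in the text available.

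The nearest rule in the protocol (Section 3, repeated in substance in Section 7) allows exclusion if "the anesthesiologist deemed it necessary that the protocol drug can not be used on the patient for any reason". Section 4 adds exclusion of patients whom the anesthesiologist judges unfit for randomization. On allocation it says "We will randomize the patients in blocks of 4", and on receipt of drug "If sevoflurane is maximized (Fe sevo >2%) and the target MAP is not achieved, then the patients will receive either esmolol or labetalol".

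On timing, the SAP gives "March 2017 – March 2018 enrollment, drug administration only during surgery" and is headed "Date: 09/04/2018".

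**The concern.** The SAP gives two incompatible pictures of who is in the comparison. The section that should settle the matter is blank in effect. If the table heads are right, some patients who received study drug are absent from the main tables, and nothing readable says why or who decided. Such a removal would come after treatment, so randomisation would no longer guarantee that the two columns are comparable.

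The two possible patterns of loss carry different implications. A loss confined to one drug is more worrying than one spread over both, and the text does not separate them. The same missing key leaves the B minus A shift without a direction.

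This matters for a null result too. Protocol Section 13 says that a finding of no difference would support continued use of both drugs without concern over visibility. That conclusion needs a stated population behind it.

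**Working it through.** Inputs: 38 enrolled, 32 treated, 17 esmolol and 15 labetalol (SAP, Study Summary and Aims); 13 and 15 (SAP, heads of Tables 1 and 2); 0.63, 0.67, 0.33, 0.37 and 1,245 per group (SAP, Sample Size Considerations).

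1. The SAP's treated count reproduces: 17 + 15 = 32. Enrolled but untreated: 38 − 32 = 6.
2. Table columns: 13 + 15 = 28.
3. Treated minus tabulated: 32 − 28 = 4, and 4/32 = 12.5%. If the heads are right, this is a minimum. It is exactly 4 if all 28 were treated, and more if any of the 28 was not.
4. Enrolled minus tabulated: 38 − 28 = 10, and 10/38 = 26.3%.
5. By arm, assuming that all 28 were treated:
   - A is esmolol: 17 − 13 = 4 lost (4/17 = 23.5%) and 15 − 15 = 0 lost.
   - A is labetalol: 15 − 13 = 2 lost (2/15 = 13.3%) and 17 − 15 = 2 lost (2/17 = 11.8%).
   
   The total is 4 either way, and the text does not choose between the two.
6. The slip reading: if 13 stands for 17, the columns are 17 + 15 = 32. They then match the treated arms with A as esmolol, and nobody is lost.
7. Does the futility calculation reveal which patients were used? With n per group = 2(1.960 + 0.842)²SD²/0.04²:
   - SDs averaged equally (pooled 0.3506) give 1,206.
   - SDs weighted by 13 and 15 (0.33 with 13) give 1,217.
   - SDs weighted by 15 and 17 (0.33 with 15) give 1,215.
   - The reverse pairings give 1,196 and 1,197.
   
   None equals 1,245. A standardised difference of about 0.1123, which rounding of the inputs allows, does give about 1,245. The 28-patient and 32-patient sets yield almost the same answer, so the stated sample size does not identify the set behind 0.63 and 0.67.
8. Timing: enrolment ended in March 2018. The SAP date is 9 April or 4 September 2018, depending on the date format, and both fall after enrolment. The SAP also already uses observed means and SDs.

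**The case against.** The strongest reply is that nothing was dropped. The tables are empty shells, Group B's 15 equals the labetalol count, and one wrong figure in Group A would explain everything. This stands as a live possibility. The 13 appears in both tables, though one head may have been copied to the other. The narrative count is consistent within itself. The text does not decide the matter, so the point has to be put as an either/or.

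A second reply is that Figure 1 may account for every patient. It may, and a reader who has the figure should look there first. A flow diagram reports what happened, however. It does not define who is to be analysed, and the section meant for that says N/A.

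A third reply is that the protocol's discretion clause permits exclusion and sets no time limit. That is fair as far as it goes. The clause is worded around patients in whom the drug cannot be used, so it does not clearly reach patients who have already received it. The clause on fitness for randomization may bear on the 6 untreated patients, whom the SAP calls enrolled, not randomised.

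A fourth reply is that the 4 had no outcome data. That alone would not explain their absence from Table 1, which lists baseline items such as age, BMI and Lund-Mackay score.

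Finally, making all randomised patients the main set is a choice. The SAP's aim is the relative efficacy of two drugs that are given only after a trigger, so the treated set has a claim to be shown as well. I accept that.

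**Conclusion.** The mismatch is certain and its cause is not. Either a table head is wrong, or at least 4 of 32 treated patients (12.5%) are outside both main tables under no rule in the readable text. The split of 4/17 and 0/15, or 2/17 and 2/15, rests on the assumption that all 28 were treated.

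A reader might infer three stronger things that the documents do not support:

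- **That four esmolol patients were removed.** This needs Group A to be esmolol and 13 to be correct, and neither is established.
- **That the results are biased or that significance would change.** Nothing in the documents shows how any omitted patients fared.
- **That the arm sizes at randomisation can be rebuilt from blocks of 4.** The SAP does not say that all 38 were randomised. Protocol Sections 1 and 14 also mention stratification, which could leave several blocks incomplete.

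The point should be fixed because it determines who is compared and the correction is cheap.

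**What to change.** First establish whether 13 is a slip for 17. If it is, correct both table heads. If it is not, replace N/A with three sets:

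1. Main set: all randomised patients who had surgery, analysed as randomised, with missing outcomes reported by arm.
2. Alongside it: the 32 treated (17 and 15), with a note that receipt of drug follows a trigger that arises after randomisation.
3. Sensitivity analysis only: the 28, with exclusion reasons by arm.

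In either case, state whether the 6 untreated patients were randomised and to which arm. Give the A/B key so that the shift has a direction, and say which set produced 0.63 and 0.67. Label the sets post hoc.

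The cost is SAP wording and rerun tables, with no new patients. There are two drawbacks.

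- **Dilution.** If all 38 were randomised, the untreated fractions were about equal and the drugs had no effect in untreated patients, the main set keeps about 32/38 = 84% of the contrast. The protocol's 110 mL would become about 93 mL. With unequal fractions the amount cannot be determined, because the contrast is between two active drugs. The treated set shows the undiluted comparison, with its own selection caveat.
- **Wide bounds for missing scores.** As an illustration, suppose 38 were randomised 19 and 19 and all 10 untabulated patients lacked scores. Best-case to worst-case bounds on the Boezaart contrast would then span 10/19 × 4 = 2.1 to 10/19 × 5 = 2.6 points, taking the scale width as 4 to 5. The SAP's minimum difference is a "1-point change on the visibility scores (Boezaart 5-point, Wormald 10-point". This is a limit on what the main set could show, not an estimate of bias.
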